The Indianapolis VAMC GRACE program has been demonstrated to improve care and outcomes for older Veterans. In a propensity weighted data analysis with 634 GRACE patients and 5614 matched control patients, GRACE was significantly associated with lower all-cause mortality after discharge from an index hospitalization: all-cause mortality 90-day post discharge was 1.3% for GRACE patients and 8.5% for control patients. However, the reach of the program is limited due to logistical constraint of the 20-mile driving distance that the GRACE teams use for their home visits. **The overall objective of the TeleGRACE project is to improve the care and outcomes of older Veterans with a recent inpatient stay by expanding access to the GRACE program, by evaluating a telehealth implementation.** Specifically, the TeleGRACE project seeks to overcome the drive-time distance barrier that currently prevents the widespread application of GRACE to eligible older Veterans by implementing virtual home visits instead of in-person home visits.

The TeleGRACE evaluation will focus on three primary aims and a secondary aim:

Primary Aim 1: To examine the effectiveness of the TeleGRACE program, we designed a randomized controlled implementation trial (RCT) powered for the primary outcome of 90-day all-cause mortality. We will also examine its effectiveness for the secondary outcomes including 90-day readmissions, 1-year ED utilization (VA and non-VA), 1-year all-cause readmissions, 1-year mortality, as well as patient, caregiver, and staff satisfaction. We hypothesize that patients who receive TeleGRACE will have lower 90-day mortality than patients in usual care.

Primary Aim 2: to examine the implementation of the TeleGRACE program. The implementation strategy is reflecting & evaluating. Implementation outcomes are based on the REAIM framework and include reach, efficacy (Aim 1), and implementation (total number of Veterans served, fidelity).

Primary Aim 3: to conduct a business-case analysis (BCA). The business case analysis will calculate the net financial savings or loss for TeleGRACE as the difference in the overall intervention costs and savings due to downstream benefits for patients receiving TeleGRACE versus usual care controls.

TeleGRACE Program Evaluation

Activity	Year-1 (FY2021)				Year-2 (FY2022)				Year-3 (FY2023)				Year-4 (FY2024)				Year-5 (FY2025)			
	Q1 OCT - DEC	Q2 JAN - MAR	Q3 APR - JUN	Q4 JUL - SEP	Q1 OCT - DEC	Q2 JAN - MAR	Q3 APR - JUN	Q4 JUL - SEP	Q1 OCT - DEC	Q2 JAN - MAR	Q3 APR - JUN	Q4 JUL - SEP	Q1 OCT - DEC	Q2 JAN - MAR	Q3 APR - JUN	Q4 JUL - SEP	Q1 OCT - DEC	Q2 JAN - MAR	Q3 APR - JUN	Q4 JUL - SEP
Program Development																				
TeleGRACE Active Implementation																				
Outcome Assessment																				
Business Case Analysis																				
Implementation Analysis																				
Effectiveness Analysis																				
Manuscripts, final reporting																				

THIS ANALYSIS PLAN FOCUSES ONLY ON EFFECTIVENESS

To examine the effectiveness of the TeleGRACE program, we designed a randomized controlled implementation trial (RCT) powered for the primary outcome of 90-day all-cause mortality. We will also examine its effectiveness for the secondary outcomes including 90-day readmissions, 1-year ED utilization (VA and non-VA), 1-year all-cause readmissions, 1-year mortality, as well as patient, caregiver, and staff satisfaction. We hypothesize that patients who receive TeleGRACE will have lower 90-day mortality than patients in usual care.

METHODS

The TeleGRACE project will be a prospective, randomized controlled trial. The unit of randomization is the patient. **This project is an evaluation of a clinical program and is classified as quality improvement and not research.**

Intervention: In-Person versus Telehealth

The GRACE program involves geriatric-focused home visits by a nurse practitioner and a social worker followed by multidisciplinary meetings to discuss each Veteran's plan of care along with ongoing collaboration with VA primary care. This "in-person" model has been in effect at the Indianapolis VA medical center since 2010. In the telehealth approach, a staff member will be trained to conduct home visits using the GRACE protocol and will use video telehealth (i.e., VA video connect [VVC]) from the patient's home to connect with the GRACE multidisciplinary team members located at the coordinating center in Indianapolis. **The use of the virtual home visit instead of the in-person home visit is the only change that is made for the TeleGRACE program.** The multidisciplinary team meetings as well as the follow-up and coordination of care with the primary care PACT teams will be unchanged. The number of visits and the content of the assessments will be the same for TeleGRACE patients as for in-person GRACE patients.

Eligible Veteran Patients

Patients eligible to receive TeleGRACE services include:

- Veterans discharged from the Indianapolis VA medical center (VAMC) for an medical/surgical diagnosis (excludes substance use disorder-related admissions; excludes planned admissions)
- Age ≥ 70 years
- Not enrolled in home-based primary care (HBPC)
- Not enrolled in hospice
- Not in dialysis
- Primary care visit within VA in the prior 2 years
- Not residing in nursing home, skilled nursing facility, or CLC
- CAN score $\geq 95^{\text{th}}$ percentile for mortality or missing CAN score
- Discharged from the hospital alive

Exclusion Criteria

- Patients who have been randomized to the control arm after their index hospitalization who become readmitted to the hospital may not be re-randomized.
- Enrolled in in-person GRACE
- Enrolled in home-based primary care (HBPC)
- Enrolled in hospice
- Enrolled in complex care program
- Dialysis (hemodialysis or peritoneal dialysis)
- Residing in nursing home, skilled nursing facility, or CLC
- Living >60 miles from the Indianapolis VAMC facility

Outcome Measures

The primary outcome for the TeleGRACE evaluation will be:

- 90-day all-cause mortality (measured as 90-days from discharge from the index hospital stay)

The secondary outcomes are:

- 90-day readmissions
- 1-year all-cause readmissions
- 1-year mortality
- 1-year ED utilization (VA and non-VA)
- 1-year falls

We will explore using time to nursing home placement as a secondary outcome. We have requested the data and will evaluate the data source for completeness; comparing it against chart review. If the team considers the data source to be accurate, then we will examine time to nursing home placement as a secondary analysis.

Randomization

Patients will be randomized in ratio of 1 (control):2 (intervention) stratified by site of primary care (Indianapolis VAMC versus non-Indianapolis [e.g., CBOCs]). We created a computer-generated randomization list (with random block sizes of 3 or 6) for each strata. With the current capacity

of VA GRACE program staff, our goal is to enroll 5 patients to TeleGRACE each month. The project will seek to enroll a total of 180 patients to TeleGRACE and 360 to usual care in a three-year recruitment period.

Data Sources

Corporate Data Warehouse (CDW) data

CDW data will be used to assess patient baseline characteristics (e.g., age, demographics, past medical history, prior healthcare utilization) as well as outcomes (i.e., ED utilization, readmission, mortality, and falls). In this way, the same data source is used to identify outcomes for both intervention and control patients.

Chart Review data

Chart review will be used to validate the TeleGRACE dose classification that is based on CDW data (see Per-Protocol analysis described below).

Follow-up Period

Patients will be followed for one year from the date of discharge from their index hospitalization. Unlike clinical trials that require in-person outcome assessments and hence implement “windows” for data collection, this evaluation will use electronic health record data for outcome assessment and hence no windows will be specified.

ANALYSIS PLAN

Intention-to-Treat Analysis

We will compare baseline characteristics between TeleGRACE patients and control patients using chi-square tests for categorical data and t-tests for continuous characteristics.

In the primary intention-to-treat (ITT) analysis, we will compare outcomes between patients randomized to usual care and those to TeleGRACE adjusting for the baseline characteristics that are significantly different by logistic regression for the binary outcome and Poisson regression for count data. If the sample size is sufficient, we will examine the effect of the TeleGRACE program by site of receipt of primary care services.

Per-Protocol Analyses

Not all patients who are randomized to receive TeleGRACE will receive services from the TeleGRACE staff. This situation is anticipated for patients who decline GRACE and others who become ineligible after discharge from the index hospitalization but before their first virtual home visit post-discharge (e.g., patients who die, get readmitted, or move to a skilled nursing facility after discharge). In the exceptionally rare case, patients may be discharged from TeleGRACE due to safety concerns for our staff (e.g., sexually or physically aggressive behavior, unwillingness to cage animals, unwillingness to store firearms). The per-protocol analyses will be similar to the planned intention-to-treat analysis but will compare the outcomes between patients who received GRACE service versus patients in usual care.

Given the expected heterogeneity in the number of TeleGRACE visits, patients will be classified into four categories as follows:

1. **Full TeleGRACE dose:** the patient received a virtual post-discharge transitional visit, followed by a virtual baseline visit with multidisciplinary team discussion, and then follow-up virtual discussion to ensure that the patient and caregiver agree with and understand the plan of care. These patients may receive additional follow-up contacts with the TeleGRACE/GRACE team members over the course of the one year follow-up period. Note: in the atypical situation where the patient did not receive a transitional visit but did receive a baseline assessment, the patient will still be classified as "full TeleGRACE dose").
2. **Transitional visit dose:** the patient received a virtual post-discharge transitional visit but did not receive a baseline visit. These patients may receive additional follow-up contacts (typically by telephone) with the TeleGRACE/GRACE team members over the course of the one-year follow-up period. In some cases, the patient may receive multiple transitional visits (e.g., after readmissions).
3. **Partial dose:** the patient received neither a post-discharge transitional visit nor a baseline visit but had other contact with the TeleGRACE/GRACE team (typically telephone visits).
4. **No TeleGRACE:** patients may have been contacted by the TeleGRACE/GRACE team in an attempt to schedule a visit, but these patients received no clinical visits or encounters. Patients who decline TeleGRACE services are included in this category. Please note: in a research randomized controlled trial, only patients who are potentially interested in participation are consented and then randomized. TeleGRACE is a quality improvement project, therefore enrollment follows procedures used in clinical care.

We will further examine the outcomes among patients across these 4 categories as well as the control patients.

Sensitivity Analyses

Considering the heterogeneity in the TeleGRACE patients, we plan to conduct the following sensitivity analyses

1. **Enrolled versus Randomized to TeleGRACE:** We will conduct the ITT analysis described above which compares patients *randomized* to TeleGRACE versus usual care controls. In addition, we will compare patients who *enrolled* in TeleGRACE versus control patients.
2. **Dose:** In addition to the description of TeleGRACE services as provided in the per-protocol analysis, the dose of the TeleGRACE program will be assessed in terms of:
 - a. The total number of GRACE contacts (telephone, virtual or in-person) in the one-year post-discharge from the index event.
 - b. Typically, home visits are conducted by a dyad of a nurse practitioner and social worker. Given staffing constraints, some patients may only receive a visit by a social worker or a nurse practitioner but not both. Therefore, each transitional, baseline, and follow-up visit will be assessed to describe whether it was conducted by social work, nursing, or other staff.
 - c. A key element of the GRACE program is the development of a multidisciplinary plan via discussion at the weekly GRACE rounds. The number of times an individual patient is discussed by the entire team in the year post-discharge will

be recorded (the geriatrician's summary of the multidisciplinary discussion will be used to identify whether a patient was discussed during team rounds).

3. **Discontinuous Eligibility Periods:** Patients who become permanently ineligible for TeleGRACE (e.g., are readmitted and then subsequently discharged to a long-term care facility) will be censored on the date they became ineligible for the outcome measures because they became ineligible for services. However, this censoring plan will be implemented retrospectively because it is expected that the older persons who will be enrolled in this study may have intermittent periods of ineligibility (e.g., during a hospital stay and then followed by short-term rehabilitation stay). Such patients may still benefit from the intervention and hence will not be censored either from the intervention or control groups.
 - a. For all intervention patients, we will calculate the proportion of eligible days a patient is cared for by the GRACE team as: the number of days that the patient was under the care of the GRACE team divided by the total number of days the patient was potentially eligible for GRACE.
 - b. We will note whether the period of eligibility was either continuous or discontinuous.
 - c. For patients with a discontinuous eligibility period, we will describe the patterns of discontinuity. For example, some patients may have a short hospital stay early post-discharge but then receive a relatively long period of GRACE services in the year post-discharge. In contrast, other patients may have recurrent hospitalizations some of which may be followed by short-term rehab stays resulting in fragmented eligibility periods of relatively short durations.
 - d. If there are more than 10% patients censored for the outcomes, we will conduct Cox-regression analysis for the hazard of death and risk-exposure adjusted Poisson regression for the number of readmissions and number of falls.

POWER

For **Aim 1** (effectiveness of TeleGRACE versus usual care), we expect to observe 2% and 8% 90-day all-cause mortality for the TeleGRACE and usual care patients, respectively. This projected effect size is conservative based on our propensity-score weighting analysis comparing GRACE patients with usual care patients. With 180 TeleGRACE and 360 usual care patients, the study has 0.96 power at detect the efficacy of TeleGRACE program with a one-sided normal test at a significance level 0.05. Considering a 10% drop-out, the analysis has 0.94 power to establish the TeleGRACE efficacy with the same effect size.

DATA MONITORING

Enrollment

We will closely monitor the randomization of TeleGRACE with the expected rate of 5 per month. We will plot the number of actual randomized patients and its expected number against the study time and update the figure on a monthly basis. Prior to the DSMB meeting, we will estimate the current randomization rate and project the final number of randomized patients by end of the fourth year with the current rate along with its 95% confidence interval based on the Poisson distribution. If the upper bound of the 95% interval is below the target number of 180. We will modify the enrollment strategy to ensure that we achieve the enrollment goal.

Interim Analysis

Since the observed effect size of in-person GRACE versus usual care is quite substantial with respect to 90-day all-cause mortality, we plan an interim analysis when a half of the enrolled patients can be evaluated for the primary outcome. One-sided normal testing will be applied for the interim analysis using O'Brien-Fleming group sequential test with the overall type error controlled at 0.05. The hypotheses are:

$$H_0: p_1 = p_2 \text{ vs. } H_1: p_1 < p_2,$$

where p_1 and p_2 stand for the 90-day all-cause mortality in TeleGRACE and usual care arms, respectively.

If the Z – test statistic crosses the boundary of -2.54 at the interim analysis, the trial will be recommended for stopping for efficacy; otherwise, the trial will continue to the end with the crossing boundary for the test statistic at -1.66. The overall power with the interim analysis for this study is 0.82.

Safety

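### The CAN mortality percentile is checked for every patient at eligibility, but it or its absence can enter the mortality models only through a chance imbalance between arms; both terms should be pre-specified

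*Combined protocol and SAP*

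**What the plan says.** Under Eligible Veteran Patients, one criterion is "CAN score $\geq 95^{\text{th}}$ percentile for mortality or missing CAN score". It therefore admits two groups: patients in the top five percentiles, and patients with no score.

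CAN does not appear again. Randomization is stratified by site of primary care only. Data Sources describes "patient baseline characteristics (e.g., age, demographics, past medical history, prior healthcare utilization", an open list of examples that does not name CAN.

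The Intention-to-Treat Analysis compares baseline characteristics between arms "using chi-square tests for categorical data and t-tests for continuous characteristics", with no stated threshold. It then compares outcomes "adjusting for the baseline characteristics that are significantly different by logistic regression for the binary outcome and Poisson regression for count data". No covariate is named there, in the per-protocol text, or for the conditional Cox model in Sensitivity Analyses item 3d.

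Mortality is the outcome at two horizons. The primary outcome is death within 90 days of index discharge, and "1-year mortality" is a secondary outcome. For 90 days the Power section says "we expect to observe 2% and 8% 90-day all-cause mortality for the TeleGRACE and usual care patients, respectively". It gives no rate or power for 1 year.

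**The concern.** The plan already holds, for each patient, either a baseline score that it describes as a percentile for mortality or the fact that the score is absent. Both are settled at eligibility screening, before allocation, so both are legitimate covariates. The stated rule decides on adjustment by whether the arms happen to differ. Under randomization that has nothing to do with whether a variable predicts death.

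So a likely predictor of the primary outcome would usually be left out and would occasionally be let in by accident, and the form of the primary model is unknown until the baseline table is run. The missing flag deserves its own term because unscored patients are the only ones not known to be in the top five percentiles. What is at stake is some precision on mortality and a model fixed in advance. Bias in the randomized comparison is not at stake.

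**Working it through.** **Inputs from the plan (Power section).** 180 TeleGRACE and 360 usual care; 2% versus 8% 90-day mortality; one-sided 0.05; stated power 0.96, or 0.94 with 10% drop-out.

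**Assumptions (not in the documents).** The threshold for a significant baseline difference is 0.05. CAN is missing in 20% of patients. Scores are spread over percentiles 95 to 99. There are three prognostic strengths: odds ratio for death per SD of score 1.35, 1.65 or 2.23, paired with odds ratio for a missing score 0.61, 0.37 or 0.22. 1-year mortality is 18% versus 25%. A smaller 90-day effect, 4% versus 8%, is also examined.

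**Step 1: reproduce the plan's power.** Unpooled one-sided test: power = Φ(|d|/SE − 1.645).
- 180/360: SE = √(0.02×0.98/180 + 0.08×0.92/360) = 0.0177; 0.06/0.0177 = 3.39; power 0.959.
- 162/324: SE = 0.0187; 0.06/0.0187 = 3.22; power 0.942.

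Both match the plan. The calculation is unadjusted.

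**Step 2: how often would CAN enter under the plan's rule?** With two independent tests at 0.05, the chance that at least one is significant is 1 − 0.95² = 0.0975. Simulation of the rule (t-test on the score, chi-square on the missing flag) gave 0.089 to 0.107 across all settings, with no dependence on prognostic strength.

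**Step 3: what does pre-specifying both terms add?** One-sided likelihood-ratio test from the logistic model at 180/360, 3,000 simulated trials per setting. The three values in each cell are for the weak, middle and strong assumption.

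| Outcome | Plan's rule | Both terms pre-specified |
|---|---|---|
| 90-day, 2% v 8% | 0.938 / 0.937 / 0.941 | 0.939 / 0.939 / 0.948 |
| 90-day, 4% v 8% | 0.570 / 0.599 / 0.575 | 0.569 / 0.598 / 0.589 |
| 1-year, 18% v 25% (assumed) | 0.586 / 0.595 / 0.597 | 0.594 / 0.613 / 0.647 |

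The differences run from −0.1 to +1.4 points at 90 days and from 0.8 to 5.0 points at 1 year. Each simulated power has a standard error of at most √(0.25/3000) = 0.009, so the smallest differences cannot be told from zero.

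**Step 4: cross-check.** Multiply the variance of the risk difference by (1 − R²), where R² is the share of outcome variance explained by score plus flag (pooled-variance test, 10% to 30% missing).
- 90 days: overall mortality at 2% v 8% is (3.6 + 28.8)/540 = 6%, where R² is 0.6% to 5.2%. At R² = 5%, power goes from 0.915 to 0.928 (2% v 8%) and from 0.550 to 0.570 (4% v 8%), a gain of 1.3 and 2.0 points.
- 1 year: at 25% mortality R² is about 2% to 16%. Power goes from 0.577 to 0.585 at R² = 2% and to 0.639 at R² = 15%, a gain of 0.8 to 6.2 points. The pooled assumed rate is (0.18×180 + 0.25×360)/540 = 22.7%, so using 25% is slightly generous.

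The two approaches together support roughly 0 to 2 points at 90 days and roughly 0 to 6 at 1 year.

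**Step 5: type I error.** With equal 8% mortality in both arms, the pre-specified model rejected in 0.050 to 0.057 of trials and the unadjusted model in 0.049 to 0.059. Adding the terms does no visible harm.

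**Step 6: events available.** At 180/360: 0.02×180 + 0.08×360 = 32.4 deaths. The Randomization section also states 1 (control):2 (intervention). At 360 TeleGRACE/180 usual care: 0.02×360 + 0.08×180 = 21.6 deaths.

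**The case against.** The strongest case against is that this hardly touches the primary outcome. At 4% versus 8%, two of the three settings show no gain at all. The larger benefit is at 1 year, where the plan claims no power and the rates used here are assumed. The eligibility rule also confines scored patients to five percentiles, which limits what the score can explain. All of this stands, and it limits the point to a cheap improvement.

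It can also be said that CAN is not excluded, since the baseline list is open and CAN could enter by the significance rule. That is true of the text, but Step 2 shows that the route is open in about one trial in ten and does not depend on prognosis. The general defect is the significance rule itself, and CAN is its clearest instance because the variable is already in hand.

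A further objection stands in part. The Power and Interim Analysis sections rest on a normal test of two proportions, with a final boundary of -1.66, whereas the intention-to-treat section uses regression. Adding CAN to the regression does not settle which test decides.

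A reader might infer more than the documents support:
- **A sizeable saving in patients at 90 days.** Applying the variance explained at 8% mortality to all 540 patients overstates it, because the TeleGRACE arm is expected at 2% and R² falls with the event rate. For an unrestricted score with log-odds slopes of 0.55, 0.75 and 1.0 per SD, R² is 2.3%, 4.5% and 8.0% at 8% mortality, but 0.7%, 1.4% and 2.8% at 2%.
- **Unscored patients at any level of risk.** They must still be 70 or over, discharged alive after an unplanned medical or surgical stay, and not in hospice or on dialysis.
- **A predictor built for 90-day death.** The plan gives no prediction horizon for CAN.
- **A check that the effect holds in high-risk patients.** About 3.6 TeleGRACE deaths are expected at 180 patients. Splitting them by CAN status cannot show this.

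**Conclusion.** The point holds as a near-free improvement. CAN status is known for every patient before allocation, yet under the stated rule it would reach the mortality models in only about 10% of trials, and then for a reason unrelated to prognosis. Under the stated assumptions, pre-specifying score and missing flag is worth roughly 0 to 2 power points at 90 days and roughly 0 to 6 at 1 year. The documents give neither CAN's prognostic strength, nor the share missing, nor 1-year rates, so these ranges illustrate the gain and do not predict it.

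The benefit appears as power for the conditional odds ratio, or as a tighter standardized risk difference. The standard error of the log odds ratio itself does not shrink. The plan's randomized comparison is not biased by the omission, and its 0.96 and 0.94 reproduce. The case for acting rests on the low cost, the possible 1-year gain, and having the model fixed before the data are seen.

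**What to change.** Add one sentence to the intention-to-treat paragraph, before any outcome comparison by arm: the 90-day and 1-year mortality models, and the Cox model of item 3d if it is used, will include the CAN mortality percentile from eligibility screening (linear, set to a constant where missing) and an indicator for a missing CAN score, whatever the baseline comparison shows. For these two terms this replaces selection by significance. The same paragraph should say whether this model or the normal test of two proportions gives the primary result, and whether a conditional odds ratio or a standardized risk difference will be reported.

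The cost is one sentence and two model parameters, with no new data collection. Those parameters are supported by about 32 expected deaths at 180/360, or about 22 at 360/180. The latter is thinner, so the conflict between the 1:2 ratio and the enrollment targets should be reconciled first. A table of deaths by arm for scored and unscored patients may be added, labelled as description only.

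### The worded allocation ratio (1 control : 2 intervention) is the reverse of the 180 TeleGRACE / 360 usual care targets, and the plan does not show which one the existing randomization list follows

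*Combined protocol and SAP*

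**What the plan says.** Three sentences of the Randomization section (under Methods) matter here. The ratio: "Patients will be randomized in ratio of 1 (control):2 (intervention) stratified by site of primary care". The list: "We created a computer-generated randomization list (with random block sizes of 3 or 6) for each strata". The targets: "The project will seek to enroll a total of 180 patients to TeleGRACE and 360 to usual care in a three-year recruitment period". The same paragraph gives the pace for the intervention arm: "our goal is to enroll 5 patients to TeleGRACE each month".

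The Power section uses the same arm sizes: "With 180 TeleGRACE and 360 usual care patients, the study has 0.96 power", for 2% versus 8% 90-day mortality with a one-sided normal test at 0.05. It adds: "Considering a 10% drop-out, the analysis has 0.94 power to establish the TeleGRACE efficacy with the same effect size".

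Under Data Monitoring, the Enrollment section tracks TeleGRACE randomization against 5 per month and a target of 180. It sets no corresponding target for controls. The Interim Analysis section says "we plan an interim analysis when a half of the enrolled patients can be evaluated for the primary outcome".

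**The concern.** The ratio sentence writes out both labels, so the order of the numbers cannot explain the conflict. It gives two intervention patients per control, while 180 and 360 give two controls per intervention patient.

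The allocation ratio is the rule from which a randomization list is generated, and this list is reported as already made. If it was generated from the sentence, the trial will not deliver the arm sizes on which its power rests. The shortfall would fall on the usual care arm, which is expected to supply most of the deaths. The enrollment monitoring would not reveal it: a reversed list could meet the TeleGRACE target of 180 while the control arm ended 270 short of 360.

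**Working it through.** **Inputs.** From the Power section: mortality 0.02 (TeleGRACE, T) and 0.08 (usual care, C), one-sided alpha 0.05 (critical value 1.645), 10% drop-out. From the Randomization section: 180 T, 360 C, 5 TeleGRACE patients per month, three years.

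**Direction of the targets.** 360/180 = 2 controls per TeleGRACE patient. The stated pace gives 5 × 36 = 180 TeleGRACE patients, which agrees with the 180 target. Blocks of 3 or 6 divide evenly under 1:2 and under 2:1, so block size does not show the direction.

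**Reproducing the plan's power.** With unpooled variance:

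- SE = √(0.02×0.98/n_T + 0.08×0.92/n_C); power = Φ(0.06/SE − 1.645).
- 180 T : 360 C: SE = 0.01770, 0.06/SE = 3.390, power = 0.960 (plan: 0.96).
- 162 T : 324 C, after 10% drop-out: 0.06/SE = 3.216, power = 0.942 (plan: 0.94).

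**If the list follows the sentence.** There are two ways to apply it.

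- TeleGRACE held at 180, hence 90 controls: SE = 0.03044, 0.06/SE = 1.971, power = 0.628. After drop-out (162:81): 0.589.
- Total held at 540, hence 360 T : 180 C: SE = 0.02153, 0.06/SE = 2.787, power = 0.873. After drop-out (324:162): 0.841. This needs 360/36 = 10 TeleGRACE patients per month, or 360/5 = 72 months at the stated pace.

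**Other variance formulas.** The plan does not name its variance. Let p̄ be the arm-weighted mean rate and SE₀ = √(p̄(1−p̄)(1/n_T + 1/n_C)). Pooled-null power is Φ((0.06 − 1.645·SE₀)/SE). Simple pooled power is Φ(0.06/SE₀ − 1.645).

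| Arms (T:C) | Unpooled | Pooled-null | Simple pooled | Expected deaths | Interim patients (deaths) |
|---|---|---|---|---|---|
| 180:360 | 0.960 | 0.915 | 0.869 | 3.6 + 28.8 = 32.4 | 270 (16.2) |
| 180:90 | 0.628 | 0.727 | 0.766 | 3.6 + 7.2 = 10.8 | 135 (5.4) |
| 360:180 | 0.873 | 0.922 | 0.956 | 7.2 + 14.4 = 21.6 | 270 (10.8) |

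Only 180:90 loses power under every formula. Exact binomial enumeration gives the same picture. With the pooled Z test it is 0.933, 0.754 and 0.942 for the three rows; with the unpooled Z test, 0.950, 0.651 and 0.917.

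**Do the stated powers settle the direction?** No. The simple pooled formula at 360:180 gives 0.956, and at 324:162 gives 0.938; these also round to 0.96 and 0.94. The overall power of 0.82 in the Interim Analysis section does not settle it either. With the stated boundaries of −2.54 and −1.66 at half information and unpooled variance, two-look power is 0.96 at 180:360, 0.63 at 180:90 and 0.87 at 360:180.

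**The case against.** The strongest reply is that this is a slip in one sentence. The arm sizes are given explicitly in two sections, and the monthly pace and the monitoring target both agree with 180 TeleGRACE patients. No text mentions 90 controls or a total of 270. The 180:90 case needs the list to follow the sentence, TeleGRACE to stop at 180 and the 360 controls to be abandoned. The loss of about one third (0.960 to 0.628) is also the largest among the three formulas: it is about 21% on the pooled-null formula and 12% on the simple pooled one. With the total held at 540, power may fall, stay level or rise, and the interim count stays at 270.

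Much of this stands. Swapped labels are the likeliest reading, and 180:90 is a worst case. The match to 0.96 and 0.94 should not be used as proof of direction. The 0.96 is also specific to the unpooled formula, even at 180:360.

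What the reply does not do is show how the list was generated. The agreement of the other figures shows what the planners intended; it does not show what the list contains. Correcting the sentence without checking the list could leave the document at odds with the trial.

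**Conclusion.** The concern holds and must be fixed. The plan gives two opposite allocation rules for a list that it says exists, and nothing in the text settles which one was used. That ambiguity is certain; any harm is conditional on the list.

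- List already 2 control : 1 intervention: no loss.
- List as worded, TeleGRACE kept at 180: power 0.63 to 0.77 depending on formula, against 0.87 to 0.96 as planned, with about 11 expected deaths instead of 32.
- List as worded, total kept at 540: twice the stated TeleGRACE pace, and a change in power whose sign depends on the formula.

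These figures rest on the plan's own 2% and 8% rates and one-sided 0.05 level.

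**What to change.** Check the computer-generated list in each stratum, then make the passages agree with it.

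- **If the list is 2 control : 1 intervention,** correct the ratio sentence to 2 (control):1 (intervention). The 180/360 targets and, on the unpooled formula, the 0.96 stand. Naming that formula in the Power section would be a useful addition. The cost is one sentence and a check of the list, with no extra patients.
- **If the list is 1 control : 2 intervention,** restate the arm sizes, the power with its variance formula, and the interim sample size for that ratio. Change the TeleGRACE monitoring target only if the TeleGRACE number changes. The cost is a less favourable stated power if TeleGRACE stays at 180.

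Restating does not recover lost power. At 1 control : 2 intervention, regaining the planned 0.96 (unrounded 0.9595) would take about 534 T : 267 C on the unpooled formula, about 450:225 on the pooled-null formula and about 368:184 on the simple pooled one. Each exceeds 180 TeleGRACE patients in three years at 5 per month. The plan does not call 0.96 a required power, so these are reference points only.
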